#### **Interview by study coordinator**

Interview of the subject by study coordinator at 1- and 2- year follow-up to assess (1) new medical conditions, (2) adverse events, (3) continued eligibility for the study, (4) medication compliance and (5) review of co-administered medications.

#### **Other assessments**

Patients will undergo the following tests at enrollment:

(1) serum creatinine to determine eligibility for the study and Apixaban dosing

## **8.2 SAFETY AND OTHER ASSESSMENTS**

1. Assessment for adverse events will be performed on an ongoing basis and at each patient visit.
2. At each study visit, the participant will be interviewed by the study coordinator to assess for adverse events. The medical records will be reviewed on an ongoing basis to identify occurrence of adverse events and hospitalizations.
3. Occurrence of medical events and addition of drugs that may affect continued eligibility for the study will be assessed at each visit. The age, creatinine and patient weight will be assessed at each patient visit to assess appropriateness of drug dosing.
4. The brain MRI will be screened for adverse events such as identification of asymptomatic intracranial bleeding after each assessment.

Definitions for a selection of important adverse events:

### *Major bleeding*

Major bleeding is defined as acute or subacute clinically overt bleeding with one or more of the following criteria: (1) Fatal bleeding and/or symptomatic bleeding in a critical area or organ, such as intracranial, intraspinal, intraocular, retroperitoneal, intraarticular or pericardial, or intramuscular with compartment syndrome (2) Bleeding causing a fall in hemoglobin level of 2 g/dL (1.24 mmol/L) or more over a 24 hr period, or (3) leading to transfusion of two or more units of whole blood or packed red cells.

### *Clinically Relevant nonmajor Bleed*

A clinically relevant minor bleed is an acute or subacute clinically overt bleed that does not meet the criteria for a major bleed but prompts a clinical response, in that it leads to at least one of the following:

- A hospital admission for bleeding, or
- A physician guided medical or surgical treatment for bleeding, or
- A change in antithrombotic therapy (including interruption or discontinuation of study drug).

### *Minor Bleeding*

All acute clinically overt bleeding events not meeting the criteria for either major bleeding or clinically relevant nonmajor bleeding will be classified as minor bleeding.

## 8.3 ADVERSE EVENTS AND SERIOUS ADVERSE EVENTS

### 8.3.1 DEFINITION OF ADVERSE EVENTS (AE)

An Adverse Event (AE) is defined as any new untoward medical occurrence or worsening of a preexisting medical condition in a clinical investigation participant administered study drug and that does not necessarily have a causal relationship with this treatment. An AE can therefore be any unfavorable and unintended sign (such as an abnormal laboratory finding), symptom, or disease temporally associated with the use of investigational product, whether or not considered related to the investigational product.

The causal relationship to study drug is determined by a physician and should be used to assess all adverse events (AE). The casual relationship can be one of the following:

Related: There is a reasonable causal relationship between study drug administration and the AE.

Not related: There is not a reasonable causal relationship between study drug administration and the AE.

The term "reasonable causal relationship" means there is evidence to suggest a causal relationship.

Adverse events can be spontaneously reported or elicited during open-ended questioning, examination, or evaluation of a subject. (In order to prevent reporting bias, subjects should not be questioned regarding the specific occurrence of one or more AEs.)

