### **Warfarin**

Dose adjusted to maintain INR between 2 – 3. Dose adjustment performed using a standardized nomogram at an anti-coagulation clinic will be encouraged but not required. Interval of INR testing will be determined by the treating physician.

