#### 10.1.5 SAFETY OVERSIGHT

Safety oversight will be under the direction of a Data and Safety Monitoring Board (DSMB) composed of one Cardiologist, one Neurologist and a biostatistician outside of the research team. Members of the DSMB will be independent from the study conduct and free of conflict of interest, or measures should be in place to minimize perceived conflict of interest. The DSMB will meet at least semiannually to assess safety data on each arm of the study. The DSMB will provide its input to the investigator and sponsor.

---

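### The ban on asking about specific adverse events has no exception for bleeding, so minor bleeds may be under-recorded, possibly more on apixaban; same scripted questions in both arms would help

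*Combined protocol and SAP*

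**What the plan says.** **The rule.** Section 8.3.1 states: "In order to prevent reporting bias, subjects should not be questioned regarding the specific occurrence of one or more AEs". The sentence before it sets out what is allowed: "Adverse events can be spontaneously reported or elicited during open-ended questioning, examination, or evaluation of a subject". No event is exempt.

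**The events.** Section 8.2 singles out bleeding for definition in three grades: major, clinically relevant nonmajor, and minor. The middle grade opens "A clinically relevant minor bleed is an acute or subacute clinically overt bleed that does not meet the criteria for a major bleed" and then requires a clinical response: admission, treatment under a physician, or altered antithrombotic therapy. Minor bleeding is any other overt bleed.

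**The occasions.** Section 8.1 schedules "Interview of the subject by study coordinator at 1- and 2- year follow-up". Section 8.2 adds: "At each study visit, the participant will be interviewed by the study coordinator to assess for adverse events". It also requires continuing review of medical records and a check of each brain MRI for silent intracranial bleeding. Section 8.3.4 has the investigator ask at each visit about events since the previous one. All of this applies to both arms.

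**Contact outside visits.** Warfarin is monitored and adjusted by the treating physician or an anticoagulation clinic (6.2), and "Interval of INR testing will be determined by the treating physician" (4.2). Apixaban is posted to patients every 6 months (6.2) and is described as needing no laboratory monitoring (2.3.2). Participants, the principal investigator and the coordinator know the treatment (6.3).

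**Use of the data.** "The DSMB will meet at least semiannually to assess safety data on each arm of the study" (10.1.5). Section 8.3.5 sends non-serious events to the DSMB every 3 months. Section 9 specifies no comparison of clinical bleeding.

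**The concern.** The trial compares two anticoagulants and carefully defines the bleeding events of interest, then forbids staff to ask about them by name. Open-ended questioning suits unexpected events. It is weaker for a known, expected event that a participant may think trivial. The recall period is about a year, longer if a visit falls late in its three-month window (8.1). Participants are aged 60 or over, with at least half to be above 70 (5.5), in a study of cognitive decline.

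The rule is the same for both arms, but opportunities for a bleed to reach a clinical record are not. A warfarin patient has INR contacts between yearly visits. An apixaban patient has no scheduled contact beyond a postal delivery. Between interviews, the DSMB's three-monthly reports must rest on record review and unprompted reports, the sources most exposed to that difference. At stake is how complete, and how comparable between arms, the recorded bleeding is when the DSMB looks at it.

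**Working it through.** The plan gives no figure for bleeding ascertainment, so there is nothing to reproduce. The check asks which events are exposed, where any asymmetry could arise, how large it could be, and which results it reaches.

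**1. Which bleeds depend on being asked about**

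| Grade (8.2) | Likely route to the database without a specific question | Exposed? |
|---|---|---|
| Major | Fatal, critical-site, haemoglobin fall or transfusion: a clinical record in either arm; MRI also finds silent intracranial bleeding | Little |
| Clinically relevant nonmajor | Admission or physician treatment normally leaves a record; a dose held or therapy changed without a visit may not | Partly |
| Minor | No such clinical response, so mainly participant report or an incidental note | Yes |

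For scale, Section 2.3.1 puts major bleeding on warfarin at 1–3% per year. With 140 patients for 2 years that is 140 × 2 × 0.01 = 2.8 to 140 × 2 × 0.03 = 8.4 events, mostly outside the problem.

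**2. What the rule alone does**

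Let the true risk be *p* in both arms and the captured fractions *d*A (apixaban) and *d*W (warfarin). The apparent ratio is (*p* × *d*A)/(*p* × *d*W) = *d*A/*d*W. A rule that lowers both fractions equally leaves the ratio at 1. It loses events without favouring either drug. A differential needs *d*A < *d*W, and its possible source is unequal contact, not the rule.

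**3. How unequal contact could be**

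The INR interval is left open. Assuming every 4 to 12 weeks, 104 weeks give 104/4 = 26 to 104/12 ≈ 9 contacts. The documents do not say whether bleeding is asked about or charted at these contacts.

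**4. Illustrative size (all capture fractions and risks assumed)**

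With *d*W = 0.90 and *d*A from 0.60 to 0.75, the apparent ratio is 0.60/0.90 = 0.67 to 0.75/0.90 = 0.83.

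The last two columns below give the chance that a two-sided 5% comparison of proportions, 140 per arm, would wrongly favour apixaban; without any differential it is 2.5%. The formula is Φ[(*p*W − *p*A − 1.96 × SE0)/SE1], where *p*W and *p*A are the recorded proportions, SE0 is the pooled and SE1 the unpooled standard error.

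| *d*A vs *d*W | Apparent ratio | True 2-year risk 6% | True 2-year risk 30% |
|---|---|---|---|
| 0.8 vs 0.9 | 0.89 | 4.2% | 8.3% |
| 0.7 vs 0.9 | 0.78 | 6.8% | 21.6% |
| 0.5 vs 0.9 | 0.56 | 16.8% | 69.5% |

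Worked case, 0.7 vs 0.9 at 30%: *p*W = 0.27 and *p*A = 0.21, or 37.8 and 29.4 expected recorded patients. The pooled proportion is 0.24, SE0 = √(2 × 0.24 × 0.76/140) = 0.0511 and SE1 = √[(0.27 × 0.73 + 0.21 × 0.79)/140] = 0.0509. Then (0.06 − 1.96 × 0.0511)/0.0509 ≈ −0.79, and Φ = 0.216. No such test is planned; the column only shows how misleading a by-arm table could be.

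**5. Where it lands**

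Section 9.4.1 models cognitive scores, MCI/dementia, infarcts and microbleeds. Cognition is tested and diagnosed by blinded staff, and the MRI is read blinded. None uses adverse-event questioning. Bleeding enters only the descriptive safety data and the DSMB's by-arm review.

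**6. What scripted questions could do**

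If they recover the same fraction *f* of missed bleeds in each arm, capture becomes *d* + *f*(1 − *d*). The gap between arms shrinks to (1 − *f*)(*d*W − *d*A) while both fractions rise, so the ratio moves towards 1 for any *f* > 0. It reaches 1 only at *f* = 1.

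**The case against.** The strongest reply is that ascertainment is broader than the rule suggests. Open-ended questions, examination, an adverse-event interview at every visit, continuing record review and MRI screening all apply to both arms. Section 2.3.3 provides education on recognising bleeding, and Section 7.1 collects reasons for stopping treatment. This stands, and it confines the problem to minor bleeds and a few nonmajor ones.

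A second reply is that naming bleeding to unblinded participants, through an unblinded coordinator, can itself distort reporting, which is the danger the rule was written to avoid. This stands as a cost. It does not favour leaving the most foreseeable events to unprompted recall, since identical wording at identical times at least makes the questioning comparable.

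A third is that scripted questions at yearly visits leave the unequal contact in place. That is correct: they reduce its effect only.

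A reader might infer more: that the rule itself creates a bias against warfarin, that warfarin records will be much fuller, or that harm will be hidden from the DSMB. The documents do not support these readings. The rule is symmetric, the INR interval and what is charted at INR contacts are unstated, and the more serious bleeds have other routes into the records.

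**Conclusion.** The point holds in a limited form. By barring specific questions without exempting its own defined bleeding events, the plan leaves minor bleeding, and some nonmajor bleeding managed without a visit, to spontaneous or open-ended report and record review. Under-recording in both arms is plausible. A larger loss on apixaban is possible, but its size is unknown and it is not a demonstrated bias. The ratios of 0.67–0.83 follow directly from the assumed capture rates and are not evidence that such a gap will occur.

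The consequence is confined to descriptive safety tables and the DSMB's by-arm review; no primary or secondary endpoint is affected. The change is worth making because it is cheap and because the rule, as written, prohibits the simplest symmetric remedy.

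**What to change.** Amend Section 8.3.1 to exempt three sets of events from the no-specific-question rule: the bleeding events defined in Section 8.2, stroke/TIA, and hospitalisation. Add to the 1- and 2-year coordinator interviews a short script, identical in both arms, asking whether each has occurred since the last visit. Keep open-ended questioning for all other events, and ask those questions first so that the script does not steer them.

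The cost is one sentence and a few questions at interviews that already exist; no visit is added and no treatment rule changes. Three downsides should be stated in the protocol:

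- recorded minor bleeds will rise;
- answers will still come from unblinded participants to an unblinded coordinator;
- unequal contact between visits will matter less but will remain, so by-arm tables of minor bleeding should carry that caveat when they go to the DSMB and in the final report.

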### 8.3.2 DEFINITION OF SERIOUS ADVERSE EVENTS (SAE)

A **Serious Adverse Event (SAE)** is any untoward medical occurrence that at any dose:

- results in death
- is life-threatening (defined as an event in which the participant was at risk of death at the time of the event; it does not refer to an event which hypothetically might have caused death if it were more severe)
- requires inpatient hospitalization or causes prolongation of existing hospitalization (see **NOTE** below)
- results in persistent or significant disability/incapacity
- is a congenital anomaly/birth defect
- is an important medical event (defined as a medical event(s) that may not be immediately life-threatening or result in death or hospitalization but, based upon appropriate medical and scientific judgment, may jeopardize the subject or may require intervention [eg, medical, surgical] to prevent one of the other serious outcomes listed in the definition above.) Examples of such events include, but are not limited to, intensive treatment in an emergency room or at home for allergic bronchospasm; blood dyscrasias or convulsions that do not result in hospitalization.)
- Suspected transmission of an infectious agent (eg, pathogenic or nonpathogenic) via the study drug is an SAE.

Although pregnancy, overdose, adverse events of special interest, and cancer are not always serious by regulatory definition, these events must be handled as SAEs.

Any component of a study endpoint that is considered related to study therapy should be reported as an SAE (eg, death is an endpoint, if death occurred due to anaphylaxis, anaphylaxis must be reported).

The following hospitalizations are not considered SAEs in BMS clinical studies:

- a visit to the emergency room or other hospital department < 24 hours, that does not result in admission (unless considered an important medical or life-threatening event)
- elective surgery, planned prior to signing consent
- admissions as per protocol for a planned medical/surgical procedure
- routine health assessment requiring admission for baseline/trending of health status (eg, routine colonoscopy)
- Medical/surgical admission other than to remedy ill health and planned prior to entry into the study. Appropriate documentation is required in these cases.
- Admission encountered for another life circumstance that carries no bearing on health status and requires no medical/surgical intervention (eg, lack of housing, economic inadequacy, caregiver respite, family circumstances, administrative reason).

---

#### 8.3.2.1 EVENTS OF SPECIAL INTEREST

In this study, the following adverse events are to be reported to BMS as serious events, regardless of whether these reports are classified as serious or unexpected:

Potential or suspected cases of liver injury including but not limited to liver test abnormalities, jaundice, hepatitis or cholestasis.

---

#### 8.3.2.2 PREGNANCY

If, following initiation of the investigational product, it is subsequently discovered that a study participant is pregnant or may have been pregnant at the time of investigational product exposure, including during at least 5 half-lives after product administration, the investigational product will be permanently discontinued in an appropriate manner (eg, dose tapering if necessary for participant).

The investigator must immediately notify [[contact]](mailto:[contact]) of this event via either the CIOMS, MedWatch or appropriate Pregnancy Surveillance Form in accordance with SAE reporting procedures.

Protocol-required procedures for study discontinuation and follow-up must be performed on the participant.

Follow-up information regarding the course of the pregnancy, including perinatal and neonatal outcome and, where applicable, offspring information must be reported on the CIOMS, MedWatch or appropriate Pregnancy Surveillance Form.

Any pregnancy that occurs in a female partner of a male study participant should be reported to BMS. Information on this pregnancy will be collected on the Pregnancy Surveillance Form. In order for Sponsor or designee to collect any pregnancy surveillance information from the female partner, the female partner must sign an informed consent form for disclosure of this information.

---

#### 8.3.2.3 OVERDOSE

An overdose is defined as the accidental or intentional administration of any dose of a product that is considered both excessive and medically important. All occurrences of overdose must be reported as an SAE.

---

### 8.3.3 CLASSIFICATION OF AN ADVERSE EVENT

---

#### 8.3.3.1 SEVERITY OF EVENT

The intensity of the adverse event will be determined by a physician on the data monitoring and safety board as:

- Mild (Grade 1): Event detected, but without any interference with activity
- Moderate (Grade 2): Some interference with activities of daily living
- Severe (Grade 3): Severe interference with activities of daily living
- Very Severe (Grade 4): Resulting in severe disability despite medical therapy

All SAEs will be grade 3 or 4 at minimum.

---

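### The rule that every SAE is at least grade 3 contradicts the plan's own severity definitions and pushes recorded severity upward for SAEs of mild or moderate intensity

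*Combined protocol and SAP*

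**What the plan says.** Section 8.3.3.1 has a physician on the safety board grade the intensity of each adverse event on four levels. The lowest level reads "Mild (Grade 1): Event detected, but without any interference with activity". The next two, grades 2 and 3, stand for partial and for severe disruption of everyday life. The top level reads "Very Severe (Grade 4): Resulting in severe disability despite medical therapy".

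The section then closes with a rule that carries no exception: "All SAEs will be grade 3 or 4 at minimum".

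Section 8.3.2 decides seriousness on other grounds. An event is an SAE if it "results in death", threatens life, leads to or prolongs an inpatient stay, causes lasting disability, or is an important medical event, among other criteria. The section goes on: "Although pregnancy, overdose, adverse events of special interest, and cancer are not always serious by regulatory definition, these events must be handled as SAEs". Section 8.3.2.1 names suspected liver injury, including abnormal liver tests, as the event of special interest, to be sent to the drug's manufacturer as serious "regardless of whether these reports are classified as serious or unexpected". Section 8.3.2.3 has every overdose reported as an SAE.

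Section 8.3.4 asks for changes in severity to be documented, so that the time an event spends at each level can be assessed.

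**The concern.** Intensity and seriousness are different attributes, and the protocol defines them separately. The floor then makes one depend on the other. Where an event is serious because of what was done about it, and not because of how strongly it affected the participant, the definitions give one grade and the floor gives another. The assessor has no rule for choosing between them, and two assessors could grade identical events differently.

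At stake is the meaning of the severity grade for SAEs. If the floor is followed, the grade of a mild or moderate SAE no longer describes its intensity, and the error always runs upward. Anyone who tabulates SAEs by severity, for the safety board or the final report, would read those events as severe.

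**Working it through.** No arithmetic in the plan needs reproducing. The check is to set the grade definitions and the floor (8.3.3.1) beside the SAE criteria (8.3.2, 8.3.2.1, 8.3.2.3) and the bleeding definitions (8.2), and ask whether one event can satisfy both rules.

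| Event | Why it is, or may be, an SAE | Grade by definition | Grade by floor | Shift |
|---|---|---|---|---|
| Nonmajor bleed leading to admission, some interference with daily life | Admission criterion, 8.3.2 | 2 | at least 3 | 3 − 2 = 1 or more |
| Overdose without symptoms | 8.3.2 and 8.3.2.3, if reporting as an SAE means classification | 1 | at least 3 | 3 − 1 = 2 or more |
| Liver-test abnormality without symptoms | 8.3.2 and 8.3.2.1, on the same condition | 1 | at least 3 | 3 − 1 = 2 or more |

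**The first row needs no special reading.** Section 8.2 lists a hospital admission for bleeding among the features that make a bleed clinically relevant but nonmajor. Section 8.3.2 makes admission an SAE criterion. Its list of hospital contacts that do not count covers short emergency visits without admission, planned or per-protocol admissions, routine health assessments and social admissions. An unplanned admission for a bleed is none of these. So an event that the protocol itself calls nonmajor must be recorded as severe or very severe.

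**The other two rows are conditional.** They hold only if the events handled or reported as SAEs are also classified as SAEs and so fall under the floor.

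**Size.** Let *p* be the share of SAEs whose intensity by definition is grade 1 or 2.

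- Share of SAEs at grade 3 or above by the definitions: 1 − *p*.
- Share recorded at grade 3 or above under the floor: 100%, whatever *p* is.
- Overstatement: 1 − (1 − *p*) = *p*.

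The documents give no value for *p* and no expected number of SAEs, so *p* could lie anywhere from 0 to 1. The figure of 100% restates the rule and does not measure the harm; the harm is *p*. Under the floor, each arm's count of SAEs at grade 3 or above simply equals its count of SAEs.

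**Duration.** If the floor applies for as long as the event is open, an SAE that eases before it resolves cannot be recorded below grade 3, and the time at grade 3 or above that 8.3.4 asks for is too long. If the floor applies only to the worst grade, this consequence falls away. The protocol does not say which is meant.

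**Search for a resolution elsewhere.** No other section exempts any SAE from the floor. The closing words of the rule hint at a level above 4, but none is defined.

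**The case against.** Several points on the other side are sound.

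- **No planned analysis uses the grade.** Section 9 contains no analysis or table by severity, and section 10.1.5 speaks only of safety data on each arm. A reader might infer that the trial's safety comparison would be wrong. The documents do not support that, because no comparison by severity is specified. Only tables that someone chooses to make, and the duration record in 8.3.4, are exposed.
- **Deaths are not lost.** Because the scale stops at disability, a reader might infer that deaths cannot be identified. But death is an SAE criterion in 8.3.2, fatal bleeding is in the major-bleeding definition in 8.2, and 8.3.4 follows events for outcome. Leaving a fatal level off an intensity scale is a choice of format.
- **Handling as an SAE may be only a reporting route.** Section 8.3.2.1 separates how liver events are sent to the manufacturer from how they are classified, and 8.3.6 treats overdose and cancer in a similar way. On that reading these events escape the floor. The documents do not settle it, so these examples stay conditional. They may also be few: the only laboratory tests the study uses are serum creatinine and, in the warfarin arm, INR, and an overdose must be both excessive and medically important.
- **Severity and seriousness do not merge entirely.** A reader might infer that they can no longer be told apart. That goes too far. The floor runs one way, a non-serious event may still be grade 3, SAEs still divide into grades 3 and 4, and seriousness has its own criteria and form. Section 8.3.4 also collects a clinician's view of severity, which may be a second record, though the protocol does not say how it relates to the board physician's grade.
- **Admission might itself count as severe interference.** If so, the floor would be redundant for admitted events. The protocol does not say this, and the scale is worded around the event's effect on the participant.

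None of this removes the conflict for an ordinary SAE that is serious because of admission and only moderate in intensity.

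**Conclusion.** The contradiction is real and follows from the text alone. An SAE of mild or moderate intensity has one grade by the definitions and a higher one by the floor. The shift is at least one grade for a grade 2 event and at least two for a grade 1 event. The number of events is unknown.

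The conclusion assumes that the floor is applied as written and that some SAEs have an intensity below grade 3; a nonmajor bleed with admission is the clearest case. Extending it to symptom-free overdoses and liver-test abnormalities needs the further assumption that they are classified as SAEs.

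The point is minor. It concerns the recorded severity of some SAEs and whatever is built on it. The primary endpoint, the sample size, the analyses in section 9 and the capture of deaths are unaffected.

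**What to change.** Delete the closing sentence of 8.3.3.1 and state that intensity is graded by the four definitions, independently of whether the event is serious. With the floor gone, the grade no longer depends on whether the events listed in 8.3.2 are classified as SAEs or only reported by that route.

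A fatal grade is optional. A sentence saying that death is recorded as an outcome would serve equally well and keeps the scale to intensity alone.

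The cost is wording in the protocol and case report form, with the IRB approval that any amendment needs. No treatment, visit or analysis changes. Any SAEs already graded under the floor should be regraded by the definitions.
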